Does this trial have therapeutic intent? Yes

A9. ClinicalTrials.gov Registration

Does this protocol/trial require registration on ClinicalTrials.gov due to it: meeting the definition of an Applicable Clinical Trial, being required under the terms and conditions of an award, or being proposed to be published in ICMJE journals? Yes

Who will be responsible for registering and maintaining the registration of this Applicable Clinical Trial? The BCM PI will register the trial because either:

- the trial is BCM PI-initiated,
- BCM is the lead site of this multicenter trial, or,
- the industry sponsor has instructed the BCM PI to register the trial, or,
- registration of this trail is required as a term and condition of the reward by the funding agency.

ClinicalTrials.gov Identifier: NCT

Section B: Exempt Request

B. Exempt From IRB Review

Not Applicable

Section C: Background Information

Critically ill patients often suffer from hospital acquired weakness. This condition may originate from Neurogenic (critical illness Polyneuropathy or CIP) or Myogenic (critical illness Myopathy or CIM) disturbances, or a combination of both (critical illness Neuro-Myopathy or CINM). Moreover, prolonged hospital stay has been associated with pronounced loss of muscle mass that can exceed 10% over the 1st week, which leads to functional impairment and complications post-hospital discharge. Prevalence of hospital-acquired weakness varies widely depending on patient population and risk factors, assessment period, diagnosis method, and patients pre-hospital functional status (age-related frailty).

Unfortunately, hospital-acquired weakness is highly prevalent among COVID-19 patients, who require paralytics for an extended period of time in order to maintain oxygenation. The prolonged use of these agents lead to long-term inhibition of the Acetylcholine receptors of Neuromuscular junctions. All COVID-19 ventilated patients at our institution have been on paralytics for at least 48 hours, and most of these patients receive concomitant Glucocorticoid therapy. Together Glucocorticoids and paralytics, lead to Myosin depletion and muscle atrophy. This combination has shown to be a risk factor for CINM. In a recent JAMA study on 5700 COVID-19 patients performed in NYC, 72% of the ventilated patients remained in the hospital, and only 3% of this population have been discharged. We believe that the major reason for this is the inability to wean from the ventilator and to rehabilitate due to Neuro-Myopathy.

A recent systematic review suggested the major pathways involved in CINM. These major pathways include muscle disuse due to prolonged immobilization, inflammation, impaired perfusion and oxygen delivery, and hyperglycemia. All these factors might be magnified among COVID-19 patients. Additional to muscle atrophy, a hyper-inflammatory systemic state and coagulation disorders induced by the COVID-19 virus, poor blood oxygen saturation, and poor perfusion to lower extremities are other important risk factors to be aware in these patients. As described above, this type of work may allow physicians to provide more personalized care and evaluate their interventions with a practical test.

Muscle weakness and fatigue impede patients; capacity to exercise, and are known to delay extubation, extend length of stay in hospital, and delay patients to achieve independent mobility. The goal of E-stim in advanced disease states is to prevent or reverse skeletal muscle wasting for persons who are not able to exercise. Conditions include advanced periods of mechanical ventilation.

A recent review including 27 papers regarding E-Stim for critical illness in hospital patients revealed a summary of E-stim characteristics which have shown to benefit this specific population. Characteristics include: a) electrode placement in lower extremity muscle groups bilaterally, hams and calf muscles; b) position for E-stim in hospital patients should be supine; and c) session frequency is effective at 5¿7 d/wk or daily until extubation or D/C from hospital. In this summary, Nussbau, et al reported a series of measurements to demonstrate the efficacy of E-stim therapy such as: thigh circumference, strength of lower extremity muscles (isometric or isotonic dynamometry, MRC score), and quality of life questionnaires. The majority of these studies selected parameters to minimize muscle fatigue. They concluded that E-stim preserves muscle strength and muscle mass, and reduces rate of muscle degradation. Also, it facilitates maintenance of functional capacity. Others have suggested that the benefit of E-stim was related to neural adaptations.

Additionally, our previous studies demonstrated that daily use of EE therapy effectively improves limb perfusion, oxygen delivery, Neuropathy, motor capacity (e.g., gait and balance), and mobility (e.g., daily number of steps). Armed with these preliminary studies, we proposed this current study to examine the effect of daily use EE therapy in critically ill COVID-19 patients. Our fundamental hypothesis is that EE therapy is effective to maintain the activation of lower extremity muscles and improve perfusion and oxygen delivery, thus preventing or reversing CINM due to prolonged hospital stay.

This is the previous study that our protocol mentions:

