Will pregnant women and/or fetuses (as described in 45 CFR 46 Subpart B) be enrolled in the research? No

E4. Neonates

Will neonates of uncertain viability or nonviable neonates (as described in 45 CFR 46 Subpart B) be enrolled in the research? No

E5. Children

Will children be enrolled in the research? No

Section F: Design/Procedure

F1. Design

Select one category that most adequately describes your research: c) Pilot

Discuss the research design including but not limited to such issues as: probability of group assignment, potential for subject to be randomized to placebo group, use of control subjects, etc.

Phase I: 20 subjects with COVID-19 infection that are being treated in the hospital. This means that this patient population is positive to COVID-19 and have been admitted with no more than 48 hours to the hospital due to severe infection. In some cases, the patients will not able to consent at the time of enrollment. This determines a high grade of severity of illness. Therefore, a family member/legal representative will be contacted via telephone for consenting. Participants will be randomized to intervention (IG) or control group (CG). The entire cohort will receive daily EE in lower extremity (e.g. Gastronemius, tibial anterior muscle) up to 1 hour. EE therapy will be provided using portable device. The EE device will be functional for IG and non-functional for CG. The duration of the study will be 2 weeks or until patient discharge, whichever comes first. The primary outcomes include between group difference and change from the baseline in muscle endurance, muscle strength, lower extremity tissue oxygen saturation, neuropathy, and muscle atrophy. Outcomes will be assessed at baseline, time of discharge or 2 weeks, whichever comes first. Due to the condition of the patient we are looking to reduce the interaction with staff, the device will be placed with no additional requirements. Physical therapy targets other physical performances, this device is aimed to improve blood flow, tissue perfusion and muscle activation while the patient is non-responsive to physical activities.

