Aim1 (to understand mechanism of action): Examine immediate benefit of lower extremity EE to improve venous return flow, tissue oxygenation, and muscle activation (short term benefit). In this study, we will recruit a convenient sample of 20 hospital patients diagnosed with COVID-19 (short-term benefit).

Optional: Subjects will be assessed using Doppler ultrasound and near infrared imaging (Kent Imaging System) at pre-, 30min, 60min, and 30min post-treatment (after stopping of EE device). Lower extremity muscle activation will be assessed by using sEMG (electromyography).

Patients will begin the study after being admitted to the hospital no more than 48 hours.

Aim 2 (to examine effectiveness): Examine effectiveness of daily use of EE to treat CINM, and other associated major adverse events (MAE) including deep vein thrombosis (DVT), cardiovascular events, and death. Participants will receive standard of care plus adjunctive daily EE therapy using an FDA approved bio-electric stimulation technology (BEST) platform (Tennant Biomodulator® PRO, AVAZZIA, Inc) during the entire length of stay in hospital. The device will be provided by the research staff.

We will assess incidence of neuropathy and myopathy during hospital discharge or 2 weeks, whichever comes first. Neuropathy severity will be quantified using vibratory perception threshold (VPT) test. Myopathy will be assessed by measuring changes in calf muscle circumstance, weight change from pre-hospital admission, and sEMG. In addition, we will determine weakness using foot dynamometer and a validated frailty meter. Length of hospital stay and MAE (documented via electronic health record) will be tracked for planning of future studies. Both extremities will have all measurements and 1 hour electrical stimulation therapy at baseline. Daily treatment will performed up to 3 times per day, but no more than 1 hour in total.

Daily electrical stimulation will be administered by a nurse/staff involved in the hospital care. A chart will be signed to register each therapy performed and will include a log of day and time of device application.

Both electrical stimulation and EMG devices will have disposable pads, after usage they will be discarded. For the Devices they will be placed inside a plastic bag that will be disposed inside the room before exiting and sanitized (wipes) based upon hospital protocols.

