Physical Activity Monitoring: The subject will be given a wearable device (PAMSys) or a smart watch, that will be measuring several parameters including number of steps taken, duration of sitting, standing, walking and lying, time taken and number of transitions from sit to stand, and walking speed for 48 hours. At the end of the specific visit, the subject will be given the device, if they are given PAMSys it will be attached to pendant to wear around the neck, otherwise they may wear the smart watch on their wrist. Investigators will provide a pre-paid envelope where the subject may place the device and send back it to the investigating team.

Oxygen Level Assessment: Oxygen saturation will be measured using a pulse oximeter.

The supervision of this study will be by pulmonary care specialists, and the location will be at Baylor College of Medicine McNair Campus.

Section G: Sample Size/Data Analysis

G1. Sample Size

How many subjects (or specimens, or charts) will be used in this study? Local: 40 Worldwide: 40

Please indicate why you chose the sample size proposed:

Sample size is convenient and selected based on available resources to demonstrate feasibility and the proof of concept effectiveness of EE therapy for COVID-19 patients admitted to ICU and post-ICU. We plan to recruit 40 eligible subjects.

G2. Data Analysis

Provide a description of your plan for data analysis. State the types of comparisons you plan (e.g. comparison of means, comparison of proportions, regressions, analysis of variance). Which is the PRIMARY comparison/analysis? How will the analyses proposed relate to the primary purposes of your study?

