P-values of 0.05 or less will be considered statistically significant based on a two-sided test unless otherwise noted. All variables will be tabulated descriptively at each scheduled time point (baseline and discharge date). For each continuous variable, the analyses will include the mean, standard deviation, minimum and maximum. For each categorical variable, the summary will include frequencies and percentages. Each variable will be analyzed using all available data. Baseline variables will be summarized using descriptive statistics. We assume that a successful intervention is also helpful to maintain subjects muscle mass, reduce neuromyopathy signs and increase venous return flow. The measured parameters (e.g. muscle circumference, sEMG, kent imaging, doppler, etc.) should change substantially from baseline to the end of the intervention. For example, the EMG amplitude values should show increased voltages. Next, for all continuous variables, pre-treatment scores will be regressed on post-treatment scores to form residualized change scores (e.g. sEMG, VPT, dynamometer, etc). Correlations will then be generated among these scores to determine whether changes in sEMG factors are related appropriately with increases in (clinically assessed) functional capacities and self-report measures of activities. ANOVA test will be used to examine significant difference between patients with severe risk factors for prolonged ICU stage (e.g. age, BMI, cardiovascular morbidities). Moderator effects will also be examined for exploratory purposes. Using gender as an example, mixed design ANOVAs will be conducted to determine whether mobility factors change over the course of treatment at different rates or with different patterns for men and women. Additional analyses will test whether changes in muscle strenght and neuropathy (e.g. VPT and dynamometer assessement at time of discharge).

Section H: Potential Risks/Discomforts

H1. Potential Risks/Discomforts

Describe and assess any potential risks/discomforts; (physical, psychological, social, legal, or other) and assess the likelihood and seriousness of such risks:

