activation. The device is used to reduce pain. However, the proposed treatment may assist in preventing or improving hospital-acquired Weakness because of prolonged hospital stay . In addition, the participation in this study may help the investigators better understand how COVID19 may impact cause myopathy and neuropathy and how to best help these patients to recover from prolonged hospital-stay .

Primary outcomes include neuropathy (assessed using VPT test); muscle function (assessed using sEMG), and tissue oxygenation (assessed using Kent Imaging). Secondary outcomes include weakness (assessed using dynamometer); muscle atrophy (assessed by weight loss as well as measuring ankle, calf, and thigh circumference); venous return flow (Doppler US [optional]); frailty (frailtymeter [optiona]); hospital length of stay (patient medical record); and major adverse events (patient health record). The primary and secondary outcomes will be assessed at baseline (if feasible) and on biweekly basis up to 4 weeks or hospital discharge, whichever came first. Appropriate mixed models (linear for continuous or Generalized Estimating Equations (GEEs) for non-continuous or non-parametric variables) will be used to test the intervention effect for each of the primary (e.g., tissue perfusion, tissue oxygen delivery, neuropathy severity, and myopathy incident) or secondary (e.g., frailty, weight loss, MAE, etc) outcomes.

Also, participation may help the investigators design a practical assessing method to identify the impact of neuromyopathy in the hospital setting. This may allow physicians to provide personalized care by monitoring muscle loss and limb complications caused by prolonged hospital length of stay.

Describe potential benefit(s) to society of the planned work.

As described above, this type of work may allow physicians to provide more personalized care for hospitalized patients in need of physical therapy for continuous and prolonged periods, specially when having a severe illness that includes medical staff risk contact.

Do anticipated benefits outweigh potential risks? Discuss the risk-to-benefit ratio.

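### Phase I baseline sEMG may be recorded under neuromuscular blockade, and the plan neither records nor handles this, so within-arm sEMG change cannot be told apart from drug offset

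*Combined protocol and SAP*

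**What the plan says.** Section C describes prolonged paralytic use as part of the problem under study, says these agents inhibit the neuromuscular junction, and states: "All COVID-19 ventilated patients at our institution have been on paralytics for at least 48 hours".

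On entry, Section F2 (Phase I, Aim 1) says: "Patients will begin the study after being admitted to the hospital no more than 48 hours". F2 also has every measurement made on both legs at baseline, and Section I adds that baseline is assessed where feasible. The inclusion criteria in F1 ask for a positive test and critical illness needing hospital care. Ventilation is neither required nor excluded.

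On the outcome, Section I lists among the primary outcomes "muscle function (assessed using sEMG". F2 uses sEMG as one of three myopathy measures, and for Aim 1: "Lower extremity muscle activation will be assessed by using sEMG (electromyography". F1 names both the between-group difference and the change from baseline as primary, though its own list does not mention sEMG. G2 expects measured parameters to change substantially from baseline and adds: "For example, the EMG amplitude values should show increased voltages".

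No section records blockade at the time of an sEMG reading, times readings around it, stratifies on it or adjusts for it.

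**The concern.** A surface EMG reading taken while the neuromuscular junction is blocked reflects the drug as well as the state of the muscle. If the block has lifted by the end reading (discharge or two weeks), amplitude rises whatever the device did. That is the pattern G2 offers as its example of success. A real loss of muscle function over the stay could be hidden by the same rise. Patients not blocked at baseline have no such offset, so an arm can mix two kinds of change score.

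At stake are one primary outcome in its change-from-baseline form, the Aim 1 mechanism reading, and the precision of the between-arm comparison in a small trial.

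**Working it through.** **1. Inputs from the documents.** Phase I has 20 patients (F1: "Phase I: 20 subjects with COVID-19 infection that are being treated in the hospital"), randomised to a functional or non-functional device. The test level is two-sided 0.05 (G2: "P-values of 0.05 or less will be considered statistically significant based on a two-sided test unless otherwise noted"). G1 says: "Sample size is convenient and selected based on available resources". There is no effect size, SD or power, so there is no figure of the plan's to reproduce. Everything below is illustration.

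**2. Assumptions.**
- 10 patients per arm (F1 gives no Phase I ratio).
- Change score with residual SD 1.
- A share *p* blocked at baseline, taken as 25–100%.
- Blocked patients gain an extra offset δ of 1 or 2 SD in either arm as the block lifts.
- A device effect *d*, either 0 or 1.32 SD. At 1.32 SD the power is about 80% when nobody is blocked.

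**3. Bias of the between-arm contrast.** The expected difference is d + δ(p₁ − p₀), where p₁ and p₀ are the expected blocked shares in the two arms. Randomisation makes these equal, so the expected difference is d. In simulation (20,000 runs per scenario) with d = 0, the rejection rate was 4.9–5.3% and the mean bias within 0.01 SD throughout.

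**4. Precision.** The variance of change within an arm is 1 + p(1 − p)δ², and the standard error of the arm difference is √(2 × variance / 10).
- p = 0.5, δ = 1: variance 1.25, SE √0.25 = 0.50, against √0.20 = 0.45 with nobody blocked.
- p = 0.5, δ = 2: variance 2.00, SE √0.40 = 0.63.

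Simulated power of an unadjusted t-test on change for d = 1.32:

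| Share blocked | δ = 1 SD | δ = 2 SD |
|---|---|---|
| 25% | 72% | 54% |
| 50% | 70% | 48% |
| 75% | 72% | 54% |

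With everyone blocked there is no mixture, and power returns to about 80%.

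**5. Change from baseline in the sham arm alone.** With no true change, its mean is pδ instead of 0. For p = 0.5 and δ = 1 that is 0.5, with SE √(1.25/10) = 0.35. The share of trials in which the sham arm shows a significant change at two-sided 0.05:

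| Share blocked | δ = 1 SD | δ = 2 SD |
|---|---|---|
| 25% | 9% | 14% |
| 50% | 23% | 50% |
| 75% | 49% | 89% |
| 100% | 80% | 100% |

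The nominal rate is 5%. The excess lies in the direction of improvement.

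**6. Chance imbalance.** With K blocked of 20, P(x in one arm) = C(K,x)·C(20−K,10−x)/C(20,10). For K = 5 or 15 the arms differ by 3 or more blocked patients with probability 0.30. For K = 10 they differ by 4 or more with probability 0.18. A split of 7 against 3 moves the observed arm difference by (4/10)δ, which is 0.4 SD for δ = 1 and 0.8 SD for δ = 2.

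**The case against.** **Timing and share.** A reader might infer that, on the protocol's own account, ventilated patients are paralysed when the baseline is taken. The documents do not say so. The 48 hours in Section C is a length of exposure, with no start time relative to admission. The 48 hours in F1 and F2 is an entry window. Overlap is plausible but not stated. The statement covers ventilated patients only. Section D speaks of bed-rest or paralytics, F1 expects only some patients to be unable to consent, and no ventilated share is given. A baseline that is not feasible may not be taken at all.

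**Control.** A reader might also infer that the sEMG outcome measures the drug wearing off instead of myopathy. The randomised sham control defeats that for the between-arm contrast (step 3). Chance imbalance is already reflected in the standard error of the test, so it is not confounding.

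**Size.** A much larger loss can be produced. Assume a change of −10 in unblocked and +80 in blocked patients, SD 20, and 30–70% blocked. The SD of change is then √(20² + p(1−p)·90²) = 46–49, and power for a 25-point effect falls from about 75% to 19–21%. That rests on a 90-point gap (4.5 SD) and an unadjusted raw change score. In simulations of this scenario with assumed starting values of 100 and 10 and an unblocked-baseline SD of 0 to 20, baseline adjustment gave 52–74% power. A blockade covariate gave about 71–75%. G2 does mention residualised change scores, but feeds them into correlations, and the mixed models in Section I do not state how baseline is handled.

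**Decision rule.** G2's voltage example is an expectation, not a criterion. No sEMG cut-off classifies a patient as myopathic, so it cannot be said that a patient still paralysed at the end would be counted as a case.

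All of this stands as a limit on the point. What remains is that change from baseline is a named primary form and that nothing in the plan deals with blockade at an sEMG reading.

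**Conclusion.** The point holds for within-arm sEMG change and for the Aim 1 activation reading. If some baselines are taken under blockade, neither can be interpreted without knowing which. With half the patients blocked and no true change, a sham arm would show a significant change in 23% (1 SD offset) to 50% (2 SD offset) of trials.

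For the randomised contrast the cost is precision and not bias: power of about 70% or about 50% instead of about 80%, for an unadjusted change score with 25–75% blocked. These figures rest on an assumed 10 per arm, assumed blocked shares and offsets, and an offset that adds equally in both arms. If blockade also blunted the response to stimulation, a device effect would be diluted, not falsely created. The plan should be changed on this point, but it does not invalidate Phase I.

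**What to change.** - Take paralytic status (on or off, and time since last dose) at each sEMG reading from the medication record. Section K already covers medications.
- Make the between-arm contrast the sole inferential sEMG analysis, adjusted for baseline and for blockade status at baseline.
- Do not interpret within-arm sEMG change, or form a change score, from a reading taken under a paralytic. For those patients, compare the off-paralytic end value between arms.
- State in advance how baselines that are not feasible will be handled.
- Report Aim 1 muscle activation separately for blocked and unblocked sessions.

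Stratifying the randomisation by paralytic use is optional with 20 patients, since a covariate serves the purpose. The cost is one extra chart field, some analysis wording and fewer sEMG change scores, with some patients contributing an end value only. No change to the clinical use of paralytics is implied.
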